11.3.2 Inclusion Criteria

Each patient **must** meet all of the following criteria:

1. Patient must be willing and able to provide written informed consent for the study.
2. Healthy male or non-pregnant female ≥ 18 years-of-age with a clinical diagnosis of moderate facial rosacea.
3. Patient must have at least eight and not more than fifty inflammatory facial lesions (i.e., papules/pustules) and ≤ 2 nodules on the face. For the purposes of study treatment and evaluation, these lesions should be limited to the facial treatment area including those present on the nose. Lesions involving the eyes, and scalp should be excluded from the count.
4. Patients must have persistent erythema on the face with moderate (3) score as per the table below:

Score	Grade	Definition
0	None	No redness present.
1	Very Mild	Slight pinkness.
2	Mild	Pink to light red.
3	Moderate	Definite redness, easily recognized.
4	Severe	Marked erythema; fiery red.

5. Patients must have a mild (1) to moderate (2) score for telangiectasia on the face as per the table below:

Score	Grade	Definition
0	Clear	No telangiectasia.
1	Mild	Only few fine vessels discernible, involves 10% or less of the facial area.
2	Moderate	Multiple fine vessels and/or few large vessels discernible, involves $> 10\% - 30\%$ of the facial area.
3	Severe	Many fine vessels and/or large vessels discernable, involves $> 30\%$ of the facial area.

6. Patients must have a definite clinical diagnosis of moderate facial rosacea (severity score 3) as per the IGE as per table below:

Score	Grade	Definition
0	Clear	No inflammatory lesions present; at most, mild erythema.
1	Almost Clear	Very mild erythema present. Very few small papules/pustules.
2	Mild	Mild erythema. Several small papules/pustules.
3	Moderate	Moderate erythema. Several small or large papules/pustules, and up to 2 nodules.
4	Severe	Severe erythema. Numerous small and/or large papules/pustules, up to several nodules.

7. Patient must be willing to minimize external factors that might trigger rosacea flare-ups (e.g., spicy foods, thermally hot foods and drinks, hot environments, prolonged sun exposure, strong winds and alcoholic beverages) during the course of the study.

8. Patient must be in general good health and free from any clinically significant disease other than rosacea on the face, that might interfere with the study evaluations.

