12.5 Statistical Analysis

12.5.1 Analysis of Primary Endpoint

Demonstration of Bioequivalence

The 90% confidence interval on the test-to-reference ratio for the mean change from baseline in inflammatory lesions will be constructed using Fieller’s method. The analysis will use the common error term from the Analysis of Variance (ANOVA) of the test and reference results with a statistical model containing terms for treatment and site.

Bioequivalence will be established if the 90% confidence interval on the test-to-reference ratio is contained within the interval [0.80, 1.25] in the PP population.

An identical analysis will be performed on the results from the mITT population to test for robustness of the findings in the PP population. A LOCF approach will be used for missing efficacy results in the mITT analysis.

Demonstration of Superiority

To ensure that the study has adequate sensitivity to a difference between products, should such a difference exist, the primary efficacy results for the test and reference treatments will each be compared to those of the vehicle treatment.

The evaluation of the superiority of the test treatment over the vehicle treatment will be conducted using ANOVA with a statistical model containing terms for treatment and center. If the mean percent change from baseline for inflammatory lesions for the test treatment is greater than, and statistically different from ($p<0.05$) that of the vehicle in the mITT population, then the test product will be considered superior to the vehicle. The results for the reference treatment will be compared to those for the vehicle in an identical manner. The same analyses will be conducted for the results from the PP population to test for robustness of the findings in the mITT population. A LOCF approach will be used for missing efficacy results in the mITT analysis.

For both the Bioequivalence and Superiority evaluations, a non-parametric rank based ANOVA will be considered when the data is highly skewed. The evaluation of skewness, (SAS® PROC UNIVARIATE) will be performed using the residuals from each ANOVA and if the skewness statistic is less than -2 or greater than +2, the analysis will be performed on the ranks of the percent change in inflammatory lesion count values.

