7.3 Demographic and Baseline Characteristics

Demographic characteristics will include:

- age;
- gender;
- race;
- ethnicity;
- Rosacea history including time since diagnosis (years).

Baseline characteristics include:

- Baseline inflammatory lesion count;
- Baseline telangiectasia assessment;
- Vital signs: systolic and diastolic blood pressure, heart rate, respiratory rate, oral body temperature;
- Physical examination: height, weight;
- Medical history other than rosacea history.

Descriptive statistics will be presented for age (years), height, weight, body mass index (BMI), time since diagnosis (years), lesion count. Frequency counts and percentages will be presented for race, ethnicity, and baseline telangiectasia grade. Height will be reported in centimeters and weight in kilograms.

Age will be derived from Informed Consent Signed Date (INFCSD) and Date of Birth (DOB) as the number of whole years between those two dates.

Demographic and baseline/randomization characteristics will be evaluated for comparability across treatment groups in the following manner. Continuous variables (age, height, and weight) will be analyzed with an ANOVA with factors of treatment and investigational site. Overall p-value for the global null hypothesis of all groups being equal will be displayed. Categorical variables (gender, ethnicity, and race) will be analyzed with a Cochran-Mantel-Haenszel general association test, stratified by investigational site.

Separately, a categorical summary will be created for physical examination results and vital signs results (normal, abnormal not clinically significant, and abnormal clinically significant). Medical history other than rosacea history will be summarized by Medical Dictionary for the Drug Regulatory Activities (MedDRA) System Organ Class and Preferred Term. Baseline vital signs and physical examination will be listed.

These analyses will be performed for Safety, mITT, and PP populations.

All parameters reported during screening or baseline phase (including informed consent information, inclusion/exclusion criteria, randomization information, method of contraception, etc.) will be presented in the by-patient listings.

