7.5.2 Analyses of Primary Endpoint

At each visit, an Investigator will assess the patient's facial rosacea by counting the number of pustules, papules, and nodules. The number of pustules, papules, total number of inflammatory lesions (pustules and papules) and nodules will be reported on the CRF.

Missing Week 12 assessments will be imputed as follows. In the mITT analysis, if a patient discontinues the study prior to Week 12 or misses the Week 12 assessment for any other reason, the LOCF rule will be used to impute the number of lesions. In the PP analysis, if a patient discontinues the study prior to Week 12, due to lack of treatment effect, after at least 8 weeks of treatment, the LOCF rule will be used to impute the number of lesions. If a patient is missing the Week 12 assessment for any other reason, the patient will be excluded from the PP population.

The baseline lesion count will be defined as the results from the latest examination prior to the start of study drug therapy. For each post-baseline visit the change from Baseline and percent change from Baseline in the total number of inflammatory lesions will be calculated. The baseline value, timepoint value, change from baseline, and percent change from baseline at the timepoint will be analyzed using descriptive statistics and will be tabulated by site, visit, and treatment group.

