7.5.2.1 Analysis of clinical equivalence of test and reference treatments

To show the clinical equivalence, estimates of mean percent change from Baseline in the inflammatory lesion count will be calculated for the Test and Reference treatment, and then the 90% CI for the mean ratio will be constructed using Fieller's method. Bioequivalence will be established if the 90% confidence interval for the ratio of Test/Reference means is contained within the interval [0.80, 1.25] for the PP population.

To this end, first an ANOVA model will be fit with percent change from Baseline in lesion count as outcome and treatment, center and treatment-by-center interaction, as factors on the data from Test and Reference treatments only (excluding Vehicle patients). If the treatment-by-center interaction factor is not significant at the 0.05 level, the model will be rerun without the interaction term. Treatment means and standard errors will be estimated from this model.

Then Fieller's formula will be applied; covariance between the treatment means will be assumed to be 0. See [Appendix 11.4](#) for complete description of the Fieller's formula.

A non-parametric rank based ANOVA will be considered when the data is highly skewed. The evaluation of skewness, (using SAS® PROC UNIVARIATE) will be performed using the residuals from ANOVA and if the skewness statistic is less than -2 or greater than +2, the analysis will be performed on the ranks of the percent change in the inflammatory lesion count values.

Analysis of bioequivalence will be performed both on the PP population and on the mITT population. The results on the PP population will be considered definitive and the results on the mITT population will be considered supportive.

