7.5.2.2 Analysis of superiority to vehicle control

The analysis of superiority will be performed separately for the Test treatment versus the Vehicle treatment and for the Reference treatment versus the Vehicle treatment. Each of these analyses will be performed using an ANOVA model with percent change from baseline in the lesion count as outcome and treatment, center and treatment-by-center interaction as factors. If the treatment-by-center interaction factor is not significant at the 0.05 level, the model will be rerun without the interaction term. The model will be fit on data from the Test and Vehicle treatment for analysis of superiority of the Test treatment and separately on data from the Reference and Vehicle treatment for analysis of superiority of the Reference treatment. From this model, the least square (LS) mean estimate for each treatment group with the 95% CI will be calculated; further, an estimate of the LS mean difference between the active treatment (Test or Reference) and Vehicle with 95% CI and the p-value for test of no difference will be calculated.

Superiority will be established if the mean percent change from Baseline (reduction) for each active treatment is estimated to be greater than, and statistically significantly different from ($p < 0.05$ for test of no difference) that for the Vehicle, for the mITT population.

Analysis of superiority will be performed both on the PP population and on the mITT population. The results on the mITT population will be considered definitive and the results on the PP population supportive.

A non-parametric rank based ANOVA will be considered under the same circumstances as for the analysis of bioequivalence.

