11.4 Code Fragments

ANOVA model for superiority analysis in primary endpoint

```
proc glm data=<datasets name>;
  class <treatment> <center>;
  model <Percent change from baseline in lesion count at week 12> = <treatment> <center>
    <treatment>*< center>/ ss3;
  lsmeans <treatment> / pdiff cl;
```

```
      output out=residuals residual=residual;
run;
quit;
```

Note: this analysis needs to be performed separately for test and reference treatments on a dataset containing only test and vehicle or reference and vehicle treatment patients. If treatment-by-center interaction term is not significant at 0.05 level, the model will be rerun without this term.

Superiority analysis in secondary endpoint

```
proc freq data=<dataset>
  tables <treatment>*<success> / fisher;
run;
```

Note: this analysis needs to be performed separately for test and reference treatments on a dataset containing only test and vehicle or reference and vehicle treatment patients.

Analysis of clinical equivalence in primary endpoint

ANOVA model:

```
proc glm data=<datasets name>;
  class <treatment> <center>;
  model <Percent change from baseline in each type of lesions at week 12> = <treatment>
    <center> <treatment>*<center>/ ss3;
  lsmeans <treatment> / stderr;
  output out=residuals residual=residual;
run;
quit;
```

Here dataset contains test and reference treatment patients only.

Note: if the treatment-by-center interaction term is not significant at the 0.05 level, the model will be rerun without this term.

Fieller's method.

Generally, Fieller's formula allows to calculate the confidence interval for the ratio of two (possibly correlated) means of two samples a and b with expectations μ_a and μ_b , and variances $\nu_{11}\sigma^2$ and $\nu_{22}\sigma^2$ and covariance $\nu_{12}\sigma^2$. If ν_{11} , ν_{12} , ν_{22} are all known, then a $(1 - 2\alpha)$ confidence interval (mL, mU) for μ_a/μ_b is given by

$$(m_L, m_U) = \frac{1}{(1-g)} \left[\frac{a}{b} - \frac{g\nu_{12}}{\nu_{22}} \mp \frac{t_{r,\alpha}s}{b} \sqrt{\nu_{11} - 2\frac{a}{b}\nu_{12} + \frac{a^2}{b^2}\nu_{22} - g \left(\nu_{11} - \frac{\nu_{12}^2}{\nu_{22}} \right)} \right]$$

where

$$g = \frac{t_{r,\alpha}^2 s^2 \nu_{22}}{b^2}.$$

Here s^2 is an unbiased estimator of σ^2 based on r degrees of freedom, and $t_{r,\alpha}$ is the α -level deviate from the Student's t-distribution based on r degrees of freedom.

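### The primary ANOVAs leave out the baseline lesion count measured on every patient, so the equivalence interval may be somewhat wider than it needs to be.

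*SAP*

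**What the plan says.** Every specification of the primary analysis has the same gap.

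- **Equivalence, SAP 7.5.2.1:** the Test/Reference ANOVA has "percent change from Baseline in lesion count as outcome and treatment, center and treatment-by-center interaction, as factors". The interaction is dropped if it is not significant at 0.05.
- **Superiority, SAP 7.5.2.2:** each active/Vehicle ANOVA has "percent change from baseline in the lesion count as outcome and treatment, center and treatment-by-center interaction as factors", with the same rule.
- **Protocol 12.5.1:** the equivalence ANOVA is run "with a statistical model containing terms for treatment and site", and the superiority ANOVA has treatment and center.
- **Code, SAP 11.4:** the superiority statement begins "model <Percent change from baseline in lesion count at week 12> = <treatment> <center>" and continues only with the interaction. The equivalence statement has the same right-hand side.

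The baseline count is available. Protocol 11.3.2 requires "at least eight and not more than fifty inflammatory facial lesions" for entry. SAP 7.5.2 fixes the value to use: "The baseline lesion count will be defined as the results from the latest examination prior to the start of study drug therapy". SAP 7.3 lists "Baseline inflammatory lesion count" among the characteristics to summarise, but the continuous variables it names for the comparability ANOVA are age, height and weight. Randomization is in blocks of three (protocol 11.8.3 and 12.2), and no stratification by baseline count is described. Neither document plans a baseline-adjusted analysis, even as a sensitivity analysis.

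**The concern.** The endpoint is percent change, so each patient's result is already scaled to that patient's own baseline. That scaling removes baseline from the mean response only if lesions fall in proportion to a baseline measured without error. Entry here depends on an observed count lying between 8 and 50. Counts near either limit will include some that were low or high by chance and will drift back, so regression to the mean can leave percent change correlated with the recorded baseline.

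Any such correlation is explained variation that the planned models leave in the error term. It matters most for equivalence, which has much less power than superiority at the plan's stated inputs. The covariate is already collected, so the precision would need no extra patients. Naming it in advance would also prevent a choice between adjusted and unadjusted results after unblinding.

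**Working it through.** **Inputs (protocol 12.1, SAP 3.2).** Mean reduction 55% on active and 40% on vehicle; SD below 47 points, taken here at 47; 224 PP patients per arm for equivalence; 280 mITT patients per arm for superiority. The limits are 0.80 and 1.25 with a 90% interval; superiority is two-sided at 0.05. The planned power is redacted, so there is no stated power to reproduce. Center terms are ignored below.

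**Step 1: equivalence without the covariate, true ratio 1.** A Fieller interval inside the limits is equivalent to two one-sided tests, of T − 0.80R and 1.25R − T.

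- Lower: (0.20 × 55) / (47 × √(1.64/224)) = 11 / 4.02 = 2.735
- Upper: (0.25 × 55) / (47 × √(2.5625/224)) = 13.75 / 5.03 = 2.735
- Critical t on 446 df: 1.648
- Power ≈ 2Φ(2.735 − 1.648) − 1 = 2 × 0.8615 − 1 = 0.723

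A simulation with 400,000 replicates gives 0.723 as well. The expected interval has g = (1.648 × 3.140/55)² = 0.0089, where 3.140 = 47/√224. The limits are therefore (1 ∓ 0.0941 × √(2 − 0.0089)) / (1 − 0.0089), or 0.875 to 1.143.

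**Step 2: superiority without the covariate.** The standard error is 47 × √(2/280) = 3.97, and Φ(15/3.97 − 1.96) = 0.965 per comparison.

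**Step 3: with the covariate.** If baseline has correlation ρ with percent change within treatment groups, the residual SD becomes 47√(1 − ρ²). Intervals narrow by about 1 − √(1 − ρ²), and the equivalent gain in patients is 1/(1 − ρ²) − 1. The values of ρ are assumptions. Joint power means equivalence plus both superiority tests.

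| Assumed ρ | Narrowing | Equivalent extra patients | Equivalence power | Joint power | Expected 90% interval |
|---|---|---|---|---|---|
| 0 | 0% | 0% | 0.723 | 0.695 | 0.875–1.143 |
| 0.1 | 0.5% | 1% | 0.728 | 0.702 | 0.876–1.142 |
| 0.2 | 2.0% | 4% | 0.746 | 0.722 | 0.877–1.140 |
| 0.3 | 4.6% | 10% | 0.777 | 0.757 | 0.880–1.136 |
| 0.4 | 8.3% | 19% | 0.819 | 0.804 | 0.885–1.130 |

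Superiority power per comparison rises only from 0.965 to about 0.977 at ρ = 0.3. The 95% half-width there falls from 7.80 to 7.44 points.

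**Step 4: which ρ is plausible.** The documents do not say. Illustrative simulations of proportional response, with baselines limited to 8–50, gave about 0.00 without counting error. With Poisson counting error they gave about 0.00 to 0.06, depending on the assumed model, and with visit-to-visit fluctuation added they reached 0.20 at most. These are assumed models, not trial data. They point to the upper rows of the table, a gain of roughly 0 to 2.5 power points.

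**Step 5: chance imbalance.** At 224 per arm, a one-standard-error difference in mean baseline is √(2/224) = 0.094 SD. It moves the ratio by ρ × 47 × 0.094/55, which is 0.008, 0.016 and 0.024 at ρ = 0.1, 0.2 and 0.3, and nothing at ρ = 0.

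**Step 6: cost in degrees of freedom.** With 448 PP patients and about 26 unpooled centers, the additive model has 448 − 1 − 1 − 25 = 421 error df. The covariate takes one of them.

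**The case against.** The strongest reply is that the plan is valid and consistent without baseline, and that the gain may be nil. Percent change is already relative to baseline, entry is restricted to IGE 3 and 8–50 lesions, and nothing in the documents supports the correlations of 0.3 to 0.4 at which the gain becomes attractive. This stands, and it limits the size of the point.

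Three stronger readings are tempting, and the documents do not support them.

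- **That chance imbalance makes the ratio wrong.** Under randomization the unadjusted standard error already allows for it. Adjustment buys precision and does not repair a bias.
- **That the coarseness of percent change proves baseline remains in the outcome.** One lesion is 12.5 points at a baseline of 8 and 2 points at 50, but this shows unequal variance. A linear covariate removes a trend in the mean and does nothing for unequal variance. Regression to the mean is the relevant mechanism.
- **That power of 0.72 shows the trial is under-sized.** The planned power is redacted and 47 is an upper bound. At SD 45 equivalence power is about 0.77 and at 43 about 0.82, so movement within the plan's own bound can outweigh the gain at ρ of 0.1 to 0.2.

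It is also fair that the change is more than one model term. Adjusted means share an estimated slope, so the zero-covariance rule in SAP 7.5.2.1 no longer fits, and the rank fallback needs its own rule. The first is met by the general Fieller formula already printed in SAP 11.4, and the second by one sentence. Neither is a material cost.

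**Conclusion.** The omission is real: no primary model uses the baseline count, and no adjusted analysis is planned. It is a missed opportunity for precision and does not affect validity. A reader might infer that the intervals are wider than needed as a matter of fact. The documents support only that they may be, because the correlation between baseline and percent change is not given.

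For assumed correlations of 0 to 0.4, the intervals narrow by 0% to 8.3% and equivalence power moves from about 0.72 to at most 0.82. This rests on mean 55, SD 47, 224 PP patients per arm and a true ratio of 1. The lower part of that range, with a gain of about 0 to 2.5 power points, is more plausible. The superiority tests benefit little. The change is worth making because its cost is close to nil even when the correlation is zero.

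**What to change.** Before unblinding:

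1. Add baseline inflammatory lesion count as a continuous covariate to the Test/Reference model (SAP 7.5.2.1), both active/Vehicle models (7.5.2.2) and the PROC GLM code (11.4). Align protocol 12.5.1, or record the departure in SAP section 8, which now reports no changes.
2. Take LS means at the common mean baseline. Put their model-based variances and covariance into the general Fieller formula in SAP 11.4, in place of the zero-covariance version.
3. Keep the unadjusted ANOVA as a pre-specified sensitivity analysis.
4. State whether the covariate, or its rank, enters the rank-ANOVA fallback.

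If the unadjusted ANOVA must stay primary, the minimum is a pre-specified baseline-adjusted sensitivity analysis, read alongside the PP baseline counts by arm.

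The cost is one error degree of freedom and slightly more SAP wording and code. No extra data or patients are needed.

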Statistical Methods:	
Analysis of Primary Endpoint
 
The percent change from baseline to Week 12 in the inflammatory (papules and pustules) lesion counts is the primary endpoint for the study. A LOCF approach will be used for imputation of missing efficacy results, where appropriate.
 
Demonstration of Bioequivalence
 
A two-way ANOVA on the test and reference results for the primary endpoint will be conducted using a statistical model containing terms for treatment and site. Bioequivalence for the primary endpoint will be established if the 90% confidence interval for the test/reference ratio of the mean percent change from baseline to Week 12 in the inflammatory (papules and pustules) lesion counts is contained within [0.80, 1.25], using the PP population. Non-parametric methods will be used if the skewness factor for the residuals from the ANOVA model are outside the range -2 to +2.
 
Demonstration of Superiority
 
To ensure that the study is sensitive enough, the test product and reference listed drug (RLD) will each be compared to the vehicle group to demonstrate their statistical superiority at $p<0.05$ (two sided) for the primary endpoint, using the mITT study population. This evaluation will be performed using separate two-way ANOVA of Test vs. Vehicle and Reference vs. Vehicle, with the statistical model containing terms for treatment and site. Non-parametric methods will be used if the skewness factor for the residuals from the ANOVA model are outside the range -2 to +2.
 
Analysis of Secondary Endpoint
 
The dichotomized Investigator's Global Evaluation (IGE) will be treated as a secondary endpoint for supportive evidence. This secondary endpoint will be evaluated as the proportion of patients with a clinical response of "success" at Week 12. Success is defined as an either IGE score 0 (clear) or 1 (almost clear) at the final visit. Any patient who is not considered a success will be considered to be a failure. A LOCF approach will be used for imputation of missing efficacy results, where appropriate.
 
Demonstration of Bioequivalence
 
Bioequivalence for the secondary endpoint will be established if the 90% continuity-corrected confidence interval for the difference in clinical

success proportions between the test and reference product is contained within the interval [-0.20, +0.20] for the PP population.

Demonstration of Superiority

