5. HYPOTHESES TESTING

Hypothesis of Equivalence (Primary Endpoint)

A two-sided, 90% confidence interval on the test/reference ratio for mean percent change from Baseline in the inflammatory lesion count will be constructed using Fieller's method. The estimates of treatment means and standard errors will be obtained from a two-way Analysis of Variance of the Test and Reference results, using a statistical model containing terms for treatment and center. Non-parametric methods will be used if the skewness factor for the residuals from the Analysis of Variance (ANOVA) model is outside the range -2 to +2. Bioequivalence will be established if the 90% confidence interval for the ratio of test/reference means is contained within the interval [0.80, 1.25].

Hypothesis of Equivalence (Secondary Endpoint)

A two-sided, continuity-corrected, 90% confidence interval on the Test-to-Reference difference for the proportion of patients with treatment success on the IGE will be constructed. Bioequivalence will be established if the 90% confidence interval for the difference is contained within the interval [-0.20, +0.20].

Hypothesis of Superiority (Primary Endpoint)

The null hypothesis to be tested is that there is no difference in the mean percent change (reduction) from baseline in the inflammatory lesion count between the active treatment and the Vehicle treatment. The hypothesis testing will be performed separately for the Test treatment versus the Vehicle treatment and for the Reference treatment versus the Vehicle treatment using ANOVA under assumption of normal error and homogeneity of variance. Only data for the relevant two treatment arms will be included in each ANOVA. Similarly, to bioequivalence, non-parametric methods will be used if the skewness factor for the residuals from the ANOVA model is outside the range -2 to +2.

Superiority will be established if the mean percent change (reduction) from Baseline in the inflammatory lesion count for each active treatment is greater than, and statistically different from ($p < 0.05$, two-sided), that for the Vehicle.

Hypothesis of Superiority (Secondary Endpoint)

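### SAP 7.5.2.1, 7.5.2.2 and Appendix 11.4 keep a treatment-by-centre term in the definitive model when p<0.05; the protocol names only treatment and site/centre terms, and SAP 8 declares no change

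*SAP*

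**What the plan says.** **Protocol.** In the synopsis, the equivalence ANOVA "will be conducted using a statistical model containing terms for treatment and site", and the two superiority ANOVAs are described "with the statistical model containing terms for treatment and site". Section 12.5.1 repeats this: equivalence uses an ANOVA "with a statistical model containing terms for treatment and site", and superiority is "conducted using ANOVA with a statistical model containing terms for treatment and center". An interaction is mentioned nowhere, and the amendment log lists no change to the model.

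**SAP 5.** Equivalence is tested "using a statistical model containing terms for treatment and center". The superiority paragraph lists no model terms; it says only that testing is done "using ANOVA under assumption of normal error and homogeneity of variance".

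**SAP 7.5.2.1, 7.5.2.2 and Appendix 11.4.** The equivalence model starts with treatment, centre and their interaction. Then: "If the treatment-by-center interaction factor is not significant at the 0.05 level, the model will be rerun without the interaction term". The means and standard errors for Fieller's formula come from whichever model is left. Superiority works the same way, with "lesion count as outcome and treatment, center and treatment-by-center interaction as factors" and the same dropping rule. Both PROC GLM fragments in Appendix 11.4 include the interaction and repeat the rule.

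**SAP 8** states that the protocol-specified analyses are unchanged.

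**The concern.** Nothing in the SAP makes the interaction exploratory or says that the model without it decides. If the test gives p<0.05, the definitive equivalence interval (PP) or superiority p-value (mITT) comes from a model that the protocol does not describe. The pre-test is run separately in the Test-Reference, Test-Vehicle and Reference-Vehicle data, so the three results can rest on different models.

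Keeping the term changes the estimate as well as the error term. The treatment difference becomes a plain average over pooled centres. SAP 7.5.1 lets a pooled centre stand with 10 PP patients and one per arm, so a thin centre can count as much as a large one. If the two models disagree on a definitive comparison, the protocol and the SAP support different answers, and SAP 8 tells the reader that no such difference exists.

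**Working it through.** **1. Model terms side by side**

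| Source | Equivalence | Superiority |
|---|---|---|
| Protocol synopsis | treatment, site | treatment, site |
| Protocol 12.5.1 | treatment, site | treatment, centre |
| SAP 5 | treatment, centre | no terms named |
| SAP 7.5.2.1 / 7.5.2.2 | plus interaction if p<0.05 | plus interaction if p<0.05 |
| SAP Appendix 11.4 | plus interaction if p<0.05 | plus interaction if p<0.05 |

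For equivalence the SAP conflicts with the protocol and with itself. For superiority the conflict is with the protocol alone.

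**2. What the kept term does.** Let d_j be the difference between arms in pooled centre j, with n_1j and n_2j patients, and K pooled centres.
- Without the interaction: difference = Σ w_j d_j / Σ w_j, with w_j = n_1j n_2j / (n_1j + n_2j).
- With the interaction: difference = Σ d_j / K.

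The two agree when centres are equal and balanced. Otherwise the second has the larger standard error.

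**3. Reference power.** The planned power is redacted, so it cannot be reproduced. From the documents' inputs (55 v 40% reduction, SD 47, 280 mITT and 224 PP per arm), ignoring centre:
- Each superiority test: 15 / (47√(2/280)) = 15/3.97 = 3.78; Φ(3.78 − 1.96) = 96.5%.
- Equivalence at a true ratio of 1: (0.20 × 55) / (47√((1 + 0.8²)/224)) = 11/4.02 = 2.735; 2Φ(2.735 − 1.645) − 1 = about 72%.

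**4. Simulation of the rule.** Each scenario had 200,000 trials. From the documents: 26 centres, 924 randomised in blocks of 3, the inputs above and the SAP 7.5.1 pooling rule. Assumed, because the documents do not give them: site sizes, and the between-centre SD of each treatment difference (0, 5 or 10 points). Fieller's covariance was set to 0 under both models, as in the SAP.

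The term was kept in 5% of comparisons at SD 0 and 7-8% at SD 5. At SD 10 it was kept in 16-17% for equivalence and 20-22% for superiority. At least one of the three definitive comparisons kept it in 13%, 19-20% and 42-44% of trials. As a check, three independent tests at SD 0 would give 1 − 0.95³ = 14%; shared arms lower this slightly.

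Equivalence power (%), SAP rule v never keeping the term:

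| Site sizes | All trials, SD 0 | All trials, SD 10 | Term kept, SD 0 | Term kept, SD 10 |
|---|---|---|---|---|
| Equal, fixed | 71.2 v 71.2 | 66.8 v 66.8 | 72 v 72 | 67 v 66 |
| Equal, random counts | 69.4 v 69.7 | 64.1 v 64.5 | 64 v 70 | 61 v 64 |
| Uneven, CV 0.5 | 66.2 v 66.8 | 59.6 v 61.1 | 55 v 67 | 52 v 61 |
| Uneven, CV 0.9 | 61.9 v 62.9 | 53.0 v 55.4 | 43 v 63 | 41 v 55 |

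The loss sits in the kept trials: at CV 0.9 and SD 0, 5% × (63 − 43) = 1.0 point, the unconditional loss. Each superiority test loses 0 to 1.8 points. Meeting all three criteria loses 0 to 3.8 points (48.0 v 51.8% at CV 0.9, SD 10).

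Error rates, SAP rule v never keeping the term:
- False equivalence at a true ratio of 0.80: 3.6-5.0% v 3.5-5.0% (SD 0); 5.6-6.4% v 5.5-6.4% (SD 10).
- False superiority, nominal 2.5% in one tail: 2.5-2.6% v 2.5% (SD 0); 3.9-4.9% v 3.9-5.1% (SD 10).

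**5. Covariance in Fieller's formula.** With the interaction kept, each LS mean averages cell means from different patients, so zero covariance is exact. Without it, both LS means share estimated centre effects, and with unequal centres they correlate (ρ). Taking equal variances V, the variance of m_t − 0.8 m_r is V(1.64 − 1.6ρ). Assuming zero therefore inflates its standard error by √(1.64/(1.64 − 1.6ρ)); the 1.25 limit gives the same factor.

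| Site sizes | ρ | SE inflation | Power, zero v fitted covariance (%) | Loss (points) |
|---|---|---|---|---|
| Equal, fixed | 0.00 | 1.00 | 71.4 v 71.4 | 0 |
| Equal, random counts | 0.04 | 1.02 | 69.7 v 71.2 | 1.5 |
| Uneven, CV 0.5 | 0.11 | 1.06 | 66.8 v 71.2 | 4.4 |
| Uneven, CV 0.9 | 0.17 | 1.09 | 63.3 v 71.3 | 8.0 |

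These are at SD 0. A separate simulation gave correlations of 0.04-0.18 and a loss of about 2 to 9 points with unequal centres. That exceeds the loss from the pre-test.

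**The case against.** **The SAP only adds detail.** The protocol asks for a model containing certain terms and does not say that others are barred. SAP 1 says the SAP supplies detail, and the rule is printed four times. So the rule is neither hidden nor chosen after the data. This stands, but a term that can change the definitive estimator is more than detail, and the clash between SAP 5 and SAP 7.5.2.1 remains.

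**Different models are already possible.** The protocol itself prescribes separate two-arm ANOVAs and a data-driven switch to ranks. This stands: differing models across comparisons are not in themselves new.

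**The sizes are assumed.** Centre sizes and heterogeneity are not in the documents. An SD of 10 points is two-thirds of the planned 15-point effect, and the 43 v 63% contrast is the most uneven pattern, conditional on a 5% event. This also stands.

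**A reader might infer that the pre-test inflates false equivalence or false superiority.** The calculations do not support this. The excess over nominal at SD 10 appears under both models, so it comes from the heterogeneity. With a larger effect SD of 15 and uneven centres (a separate run of 4,000 trials per scenario), the SAP rule gave less false superiority than the model without interaction: 6.3 v 7.8% with 26 centres and 6.8 v 9.1% with 18.

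**Dropping the interaction does not by itself restore the protocol's analysis.** Centre pooling is in SAP 7.5.1 only, and zero covariance is least accurate in exactly the model to be preferred. Both points stand and shape the fix.

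**Disclosure would be enough.** Since the main harm is the undeclared departure, declaring the rule is a defensible alternative. It would leave the data-dependent choice of estimator and its power cost in place.

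**Conclusion.** The inconsistency is established from the text alone and should be corrected; it does not invalidate the trial. The main harm is an undeclared departure in the model behind all three definitive primary comparisons, with an internal SAP contradiction for equivalence.

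The numerical cost is small on average: about 0 with equal fixed centres, up to about 2.5 points of equivalence power and 3.8 points for all three criteria with very uneven centres. It is concentrated in trials where the term is kept. These figures rest on the assumed site sizes, a between-centre effect SD of 0 to 10 points, a true ratio of 1 and normal errors with SD 47.

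Three stronger readings are not supported: that the rule was chosen after seeing data, that it materially raises false-positive rates, and that SAP 5 also contradicts SAP 7.5.2.2 on superiority.

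**What to change.** 1. In SAP 7.5.2.1, 7.5.2.2 and both GLM fragments, take the definitive interval and p-values from treatment plus centre without the interaction in all cases. Report the interaction test and by-centre estimates as supportive, and say that they do not change the definitive model.
2. Name the same terms in the SAP 5 superiority paragraph.
3. Take the covariance of the two LS means from the fitted model and use the general Fieller formula already printed in Appendix 11.4.
4. In SAP 8, declare centre pooling, which the protocol does not mention. If the sponsor keeps the conditional rule, declare that too and align both SAP 5 paragraphs with it.

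The cost is wording and a few lines of code, with no new data. A real interaction would be described rather than built into the primary estimate, and larger centres would carry more weight in the treatment difference. At CV 0.9 and SD 10, false superiority moves from 4.9 to 5.1%; the SD 15 run above shows a larger gap. Using the fitted covariance removes an accidental conservatism in the equivalence interval. Where effects truly vary by centre, false equivalence, already above 5% under either model, would rise somewhat further. Declaring the rule without changing it costs a paragraph in SAP 8 and edits to SAP 5.
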